6.1.1. Statistical Analysis

All analyses will be performed by QST using SAS® Version 9.3 or later. All summary tables and data listings will be prepared utilizing SAS® software.

The standard operating procedures (SOPs) of QST will be followed in the creation and quality control of all data displays and analyses.

6.1.2. Baseline Definition

Baseline is defined as the last non-missing assessment prior to first dose of study drug.

6.1.3. Visit Mapping

Data will be summarized based on nominal visit indications with the exception of data captured at early termination and unscheduled visits. Data from early termination and unscheduled visits will be summarized based on mapped visit values. The analysis windows for early termination and unscheduled visits are presented in the following table.

Analysis Windows for Efficacy and Safety Assessments

Scheduled Visit	Target Study Day	Analysis Window (Days)
Day 8	8	4 to 11

Day 15	15	12 to 18
Day 22	22	19 to 30

Data collected at early termination and unscheduled visits prior to study day 4 will not be analyzed, with the exception of those identified as baseline values. Data collected at early termination and unscheduled visits after study day 30 will not be included in the analyses.

The definition for the study day included in each analysis window is defined as below:

Study Day prior to Baseline Visit = Visit Date – Baseline Visit Date

Study Day on or after Baseline Visit = Visit Date – Baseline Visit Date + 1

If an assessment's mapped visit is a visit at which the subject has data from a scheduled visit, or if no analyses are planned for the assessment at the mapped visit, the data collected at the early termination or unscheduled visit will not be included in analyses.

In the event of multiple values from unscheduled or early termination assessments within an analysis window, the value closest to the scheduled visit target study day will be used for analyses. If two values tie as closest to the time point (for example, one value is before and the other value is after the time point), then the later value will be selected.

Data collected at all visits will be included in the data listings with visit presented as reported by the site.

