## 4.3 Subject Completion

The subject has completed the study when the Test of Cure Visit is completed. Subjects who require further follow-up for an AE will be followed according to [Section 8.4](#).

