## 4.4 Subject Discontinuation

A subject MAY be withdrawn from the study (at the discretion of the investigator, sponsor, and/or IRB) prior to study completion for any of the following reasons, including, but not limited to:

- A serious adverse event (SAE) occurring during the course of the study which precludes continued follow-up
- Intercurrent illness which may, in the investigator's opinion, significantly affect study assessments
- Failure to follow required study procedures

A subject MUST be discontinued prior to the final study visit for any of the following reasons:

- Whenever the subject decides it is in his/her best interest to withdraw
- Whenever the investigator decides it is in the subject's best interest to be withdrawn

Prior to discontinuing a subject, every effort should be made to contact the subject, schedule a final study visit, and obtain as much follow-up data as possible. If possible, the assessment schedule for the Test of Cure Visit should be performed, and an effort should be made to collect all study drug.

Due to the time required to obtain fungal culture results from Screening/Baseline, subjects will be enrolled into the study based on a clinical diagnosis of otomycosis (including the visible presence of fungal elements at Screening/Baseline), without a requirement for a positive fungal culture. Subjects who end up with a negative Screening/Baseline fungal culture will not be discontinued from the study, but these subjects will not be included in the primary efficacy analysis. Because the sponsor's goal is to obtain approximately 10 subjects per group who meet both criteria of having a positive fungal culture at Screening/Baseline and completing the Test of Cure Visit, the number of subjects enrolled into the study may be adjusted depending on the rates of negative fungal culture at Screening/Baseline and of discontinuation or loss to follow-up.

Subject discontinuations will be documented clearly on the applicable electronic case report form (eCRF). Subjects who discontinue from the study will not be replaced, but additional subjects may be enrolled and randomized if it appears that approximately 75 subjects is insufficient to meet the sponsor's goal of approximately 10 subjects per group who meet both criteria of having a positive fungal culture at Screening/Baseline and completing the Test of Cure Visit.

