### **6.4 Test of Cure**

This visit may occur up to 1 day sooner or up to 8 days later than the specified day. Subjects randomized to the 7-day group will have the Test of Cure Visit on Day 15, and subjects randomized to the 14-day groups will have the Test of Cure Visit on Day 22.

The following procedures and evaluations will occur during the Test of Cure Visit:

- Otomycosis signs and symptoms
- Subject global assessment
- Microbial (fungal) culture
- AE evaluation
- Review of concomitant medications
- Urine pregnancy test (in female subjects of childbearing potential only)

In case of early termination, the procedures planned for the Test of Cure Visit should be performed if possible.

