## **6.5 Unscheduled Study Visits**

Additional visits may be scheduled, as necessary, to ensure the safety and well-being of subjects. All additional examinations should be fully documented in the source files and eCRFs, as appropriate. Visits that fall outside the designated scheduled visit window but that are intended to fulfill scheduled visit requirements will be collected and transcribed to the appropriate scheduled visit eCRF.

If a subject is seen for multiple visits during a given visit time frame, the data from the visit(s) that are intended to meet the protocol requirements for the scheduled visit should be captured on the visit eCRF. Any other data from any additional visits within a scheduled visit interval will be captured elsewhere on the eCRF.

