## **6.7 Missed Visits**

If a subject misses any scheduled follow-up visit and cannot be seen prior to the start of the visit range for the next scheduled follow-up visit, the visit is considered missed.

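### SAP 6.1.3 uses one visit-window table for all arms, so an in-window early-termination or unscheduled Test of Cure record on Days 19–23 in the 7-day arm maps to a visit that arm does not have; few records, possibly none, are affected

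*SAP*

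**What the plan says.** SAP 6.1.3 summarises scheduled visits under their nominal label and maps only early-termination and unscheduled records. One table serves every arm: Days 4–11 map to Day 8, Days 12–18 to Day 15 and Days 19–30 to Day 22.

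A mapped record gives way to scheduled data at the same visit. In addition, "if no analyses are planned for the assessment at the mapped visit, the data collected at the early termination or unscheduled visit" are not analysed. A separate sentence sets an outer limit: "Data collected at early termination and unscheduled visits after study day 30 will not be included in the analyses". All visits stay in the listings.

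Test of Cure falls on Day 15 in the 7-day arm and Day 22 in the 14-day arms (SAP 6.7.1). Protocol 6.4 gives its window: "This visit may occur up to 1 day sooner or up to 8 days later than the specified day". SAP 6.4.3 repeats -1/+8 in the per-protocol criteria. The notes to the SAP table shells (for example Table 14.2.2.3.1) list only Day 8 and Day 15 as follow-up visits for the 7-day arm. Missing Test of Cure components are filled by LOCF (SAP 6.1.5).

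For subjects who withdraw, Protocol 4.4 says that "every effort should be made to contact the subject, schedule a final study visit, and obtain as much follow-up data as possible", and Protocol 6.4 adds: "In case of early termination, the procedures planned for the Test of Cure Visit should be performed if possible".

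**The concern.** The table is indexed by calendar day, but the role of a day depends on the arm. Day 15 is End of Treatment in the 14-day arms and Test of Cure in the 7-day arm. Day 22 is Test of Cure in the 14-day arms and nothing in the 7-day arm. The Day 15 and Day 22 rows therefore fit only the 14-day schedule. The Day 8 row fits both, because its upper limit of 8+3 is also the protocol limit for End of Treatment in the 7-day arm.

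A 7-day subject who withdraws and is seen on, say, Day 20 can have every component of therapeutic cure recorded inside the permitted Test of Cure window. SAP 6.1.3 sends that record to Day 22, while SAP 6.4.3 would treat a Test of Cure on the same day as in window. MITT membership does not require completion (SAP 6.4.2), so the subject stays in the primary analysis with an earlier, carried-forward value. This can happen only in the 7-day arm, on one side of the descriptive 7-versus-14-day comparison that is a stated objective.

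**Working it through.** **The plan's own figure.** In the 14-day arms, Test of Cure is Day 22 with +8, so 22 + 8 = Day 30. This matches the 30-day study duration in Protocol 3.3 and the upper limit of the Day 22 row. The table reproduces the 14-day schedule correctly.

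**Inputs.** Test of Cure target days: SAP 6.7.1. Window -1/+8: Protocol 6.4. End of Treatment window of up to 3 days late: Protocol 6.3. Last scheduled dosing days, 7 and 14: Protocol 6.2.1. Mapping rows: SAP 6.1.3.

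| | 7-day arm | 14-day arms |
|---|---|---|
| Permitted Test of Cure days | 15-1 to 15+8 = 14–23 (10 days) | 22-1 to 22+8 = 21–30 (10 days) |
| Row that maps to Test of Cure | Day 15 row, 12–18 | Day 22 row, 19–30 |
| Permitted days not mapped to Test of Cure | 19–23 (5 of 10) | none (0 of 10) |

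**Same interval after dosing.** Days 19–23 in the 7-day arm are 19-7 to 23-7 = 12–16 days after the last scheduled dose. The equivalent in the 14-day arms is 14+12 to 14+16 = Days 26–30, which maps to Test of Cure and is kept.

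**What LOCF would use.** Assume no nominal Test of Cure value and no mapped value from Days 12–18. The last usable 7-day observation is then normally End of Treatment, on Day 8 to 8+3 = Days 8–11. That is 1–4 days after the last scheduled dose, in place of a value 12–16 days after it.

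**Weight of one subject.** If the carried-forward outcome differs from the observed one, the 7-day MITT rate moves by 1/n. SAP 6.1.6 removes the 7-day kits once at least 10 MITT subjects are in that arm: 1/10 = 10.0 points. If all of 75/3 = 25 subjects were culture-positive: 1/25 = 4.0 points.

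**Check of the proposed window.** With Test of Cure on Days 12–23 in the 7-day arm and Days 19–30 in the 14-day arms, both windows are 12 days wide. Both cover 5–16 days after the last scheduled dose (12-7 to 23-7; 19-14 to 30-14). No value now used is displaced: scheduled data still take precedence, and the closest-to-target rule prefers Days 12–18 (at most 3 days from Day 15) to Days 19–23 (4–8 days away).

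**The case against.** The strongest objection is that almost no record can meet the conditions. Mapping does not touch scheduled visits. A 7-day subject who attends on Days 19–23 for the Test of Cure procedures is inside the protocol window and would ordinarily be entered as Test of Cure. Protocol 4.3 then applies: "The subject has completed the study when the Test of Cure Visit is completed". Protocol 6.5 goes further: "Visits that fall outside the designated scheduled visit window but that are intended to fulfill scheduled visit requirements will be collected and transcribed" to the scheduled-visit eCRF. Nor does lateness alone lose the visit. Under Protocol 6.7, if a subject who misses a visit "cannot be seen prior to the start of the visit range for the next scheduled follow-up visit, the visit is considered missed", but no visit follows Test of Cure in this arm. Harm needs a final visit labelled early termination or unscheduled, no other Test of Cure value, and a carried-forward outcome that differs from the observed one. This objection stands, and it is why the point ranks low. It does not empty the case, because the plan asks withdrawing subjects for exactly such a visit and gives early-termination data their own mapping.

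Second, the exclusion is inferred. The SAP does not say that 7-day records on Days 19–23 are dropped. That is also right. The alternative is to count a mapped Day 22 as Test of Cure in the 7-day arm, which conflicts with SAP 6.7.1. If both readings are open, two programmers could derive different primary outcomes from one record, so the text still needs correcting.

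Third, a reader might infer from 5 of 10 days that half of the 7-day Test of Cure data are at risk. The documents do not support that. The ratio counts calendar days, and nominal visits on those days are unaffected. Likewise, 10.0 points is the weight of any one subject at n=10, not an expected effect.

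**Conclusion.** The point holds as a small correction. The Day 15 and Day 22 rows of SAP 6.1.3 give a wrong result for an early-termination or unscheduled record on Days 19–23 in the 7-day arm. The conclusion rests on one inference: that no Day 22 analysis is planned for that arm, as the shell notes imply.

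The number of affected records is unknown and may be zero. The effect per changed outcome is 1/n, between 4.0 and 10.0 points for n from 25 down to 10. The active-versus-vehicle comparison over 14 days is untouched, and no hypothesis is tested. The per-protocol analysis is largely untouched, since it drops subjects who did not attend Test of Cure apart from certain discontinuations.

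A reader might infer two further things. One is that the rule biases the comparison against the shorter course; the documents do not show whether a carried-forward End of Treatment value would be better or worse than the one it replaces. The other is that the Day 30 limit must also be shortened for the 7-day arm. Under the same inference, Days 24–30 in that arm already fall outside its visit-based analyses, so a shorter limit gains nothing. Read literally, it could remove adverse-event data from visits on those days, which the present sentence keeps.

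**What to change.** Before database lock, and without reference to outcomes in the open-label 7-day arm, make the table in SAP 6.1.3 arm-specific:

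- 7-day arm: End of Treatment Days 4–11, target Day 8; Test of Cure Days 12–23, target Day 15.
- 14-day arms: rows unchanged, labelled On Treatment Days 4–11, End of Treatment Days 12–18, Test of Cure Days 19–30.

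The upper limit of 23 is 15+8. The early side stays at -3 days, as in the current table. That is a choice for consistency across arms; the protocol window itself opens on Day 14.

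Leave the sentence on data after Day 30 as it is. If a Day 23 limit is stated for the 7-day arm, confine it to visit-based efficacy summaries so that no adverse-event data are excluded.

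The cost is one table in the SAP. No extra data are collected and nothing changes for subjects.

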6.1.4. Adjustments for Covariates

Not applicable to this study.

6.1.5. Handling of Dropouts or Missing Data

Missing values from the Test of Cure visit from which the dichotomized Therapeutic Cure is derived will be imputed using LOCF method.

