**Table 1 Study Schedule**

| Evaluations and Procedures:          | Screening/
Baseline
Day 1 | On
Treatment a
Day 8 c | End of
Treatment a
Day 8 or 15 d | Test of
Cure b
Day 15 or 22 e |
|--------------------------------------|---------------------------------|--|--|---|
| Informed consent/assent              | X                               |  |  |   |
| Inclusion/exclusion criteria         | X                               |  |  |   |
| Medical/medication history           | X                               |  |  |   |
| Physical examination                 | X                               |  |  |   |
| Otomycosis signs and symptoms        | X                               | X  | X  | X   |
| Urine pregnancy test f    | X                               |  |  | X   |
| Randomization                        | X                               |  |  |   |
| Dispensation of study drug           | X                               |  |  |   |
| Dispensation of subject diary        | X                               |  |  |   |
| Collection of subject diary          |                                 | X  | X  |   |
| Administration of study drug at site | X                               |  |  |   |
| Weighing of study drug               | X                               | X  | X  |   |
| Collection of study drug             |                                 |  | X  |   |
| Subject global assessment            | X                               | X  | X  | X   |
| Microbial culture g       | X                               |  | X  | X   |
| Ear cleaning                         | X                               | X  | X h   |   |
| AE evaluations                       | X                               | X  | X  | X   |
| Concomitant medications review       | X                               | X  | X  | X   |

- a. This visit may occur up to 3 days later than the specified day.
- b. This visit may occur up to 1 day sooner or up to 8 days later than the specified day.
- c. For subjects randomized to the 14-day durations, the Day 8 visit constitutes an On Treatment Visit; for subjects randomized to the 7-day group, the Day 8 visit constitutes the End of Treatment Visit with those procedures performed instead

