- d. The End of Treatment Visit is scheduled to occur on Day 8 for subjects randomized to the 7-day treatment duration, and on Day 15 for subjects randomized to the 14-day treatment durations
- e. The Test of Cure Visit is scheduled to occur on Day 15 for subjects randomized to the 7-day treatment duration, or on Day 22 for subjects randomized to the 14-day treatment durations. In case of early termination, the assessments planned for the Test of Cure Visit should be performed if possible
- f. Females of childbearing potential only
- g. For both fungi and bacteria at the Screening/Baseline visit and for fungi only at the End of Treatment and Test of Cure visits
- h. To be performed in subjects randomized to the 7-day group only, and after all efficacy assessments (otomycosis signs and symptoms, subject global assessment, and microbial culture) have already been performed

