### **10.5.4 Missing Data**

Missing values from the Test of Cure visit from which the dichotomized Therapeutic Cure is derived will be imputed using last observation carried forward (LOCF) method.

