6. STATISTICAL AND ANALYTICAL PLANS

6.1. General Methodology

All statistical processing will be performed using SAS® unless otherwise stated. No interim analyses are planned.

No formal hypotheses will be tested in this study. Descriptive comparisons will be made between the micronazole oil and the oil vehicle groups for subjects randomized to the 14-day groups. Additionally, descriptive comparisons will be made between the 7-day and 14-day groups for subject's randomized to the miconazole oil treatment.

Descriptive statistics will be used to provide an overview of the efficacy and safety results. For categorical parameters, the number and percentage of subjects in each category will be presented. For continuous parameters, descriptive statistics will include n (number of subjects), mean, standard deviation (SD), median, minimum, and maximum.

The primary method of handling missing efficacy data will be the method of last observation carried forward (LOCF) imputation.

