None	xx (xx.x%)	xx (xx.x%)	xx (xx.x%)
Mild	xx (xx.x%)	xx (xx.x%)	xx (xx.x%)
Moderate	xx (xx.x%)	xx (xx.x%)	xx (xx.x%)
Severe	xx (xx.x%)	xx (xx.x%)	xx (xx.x%)

Note: Table only includes assessments of the study ear.

SOURCE: USERNAME\SPONSOR\PROJECT\JOBNAME (DATE,TIME)

Table 14.1.2.3: Subject Baseline Characteristics
(Safety Population)
(Page 2 of 2)

	7-Day Miconazole Oil (N=xx)	14-Day Miconazole Oil (N=xx)	14-Day Vehicle Oil (N=xx)
Debris			
n	xx	xx	xx
None	xx (xx.x%)	xx (xx.x%)	xx (xx.x%)
Scant	xx (xx.x%)	xx (xx.x%)	xx (xx.x%)
Moderate	xx (xx.x%)	xx (xx.x%)	xx (xx.x%)
Heavy	xx (xx.x%)	xx (xx.x%)	xx (xx.x%)
Presence of Fungal Elements			
n	xx	xx	xx
Absent	xx (xx.x%)	xx (xx.x%)	xx (xx.x%)
Present	xx (xx.x%)	xx (xx.x%)	xx (xx.x%)
Pain			
n	xx	xx	xx
Absent	xx (xx.x%)	xx (xx.x%)	xx (xx.x%)
Present	xx (xx.x%)	xx (xx.x%)	xx (xx.x%)
Subject Global Assessment			
n	xx	xx	xx
None	xx (xx.x%)	xx (xx.x%)	xx (xx.x%)
Minor	xx (xx.x%)	xx (xx.x%)	xx (xx.x%)
Moderate	xx (xx.x%)	xx (xx.x%)	xx (xx.x%)

Note: Table only includes assessments of the study ear.

SOURCE: USERNAME\SPONSOR\PROJECT\JOBNAME (DATE,TIME)

Statistical Analysis Plan

Hill Dermaceuticals, Inc. HD-MCZ-PHII-DRF062016

Version: 1

Date: 30 MAY 2019

Table 14.2.1.1: Summary of Primary Efficacy Endpoint: Therapeutic Cure at Test of Cure
 (Modified Intent-to-Treat Population)

	7-Day Miconazole Oil (N=xx)	14-Day Miconazole Oil (N=xx)	14-Day Vehicle Oil (N=xx)
Therapeutic Cure ^a at Test of Cure			
Achieved	xx (xx.x%)	xx (xx.x%)	xx (xx.x%)
Not Achieved	xx (xx.x%)	xx (xx.x%)	xx (xx.x%)

^a Therapeutic Cure is defined as a negative mycological culture plus Clinical Cure for the study ear. Clinical Cure is defined as the absence of all otomycosis signs and symptoms based on Investigator assessment according to the scales for each individual sign or symptom and with absence defined as a score of 0 on each of the scales for pruritus, debris, fungal elements, and pain.

Note: Last observation carried forward (LOCF) used to impute missing values.

SOURCE: USERNAME\SPONSOR\PROJECT\JOBNAME (DATE,TIME)

Statistical Analysis Plan

Hill Dermaceuticals, Inc. HD-MCZ-PHII-DRF062016

Version: 1

Date: 30 MAY 2019

Table 14.2.1.2: Summary of Primary Efficacy Endpoint: Therapeutic Cure at Test of Cure
(Per-Protocol Population)

	7-Day Miconazole Oil (N=xx)	14-Day Miconazole Oil (N=xx)	14-Day Vehicle Oil (N=xx)
Therapeutic Cure ^a at Test of Cure			
Achieved	xx (xx.x%)	xx (xx.x%)	xx (xx.x%)

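### LOCF can report therapeutic cures never seen at Test of Cure and scores a Day 8 dropout differently by treatment duration; no MITT table gives composite cure without it

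*SAP*

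**What the plan says.** SAP 6.1.5 gives the rule for the primary endpoint: "Missing values from the Test of Cure visit from which the dichotomized Therapeutic Cure is derived will be imputed using LOCF method". Protocol 10.5.4 agrees ("will be imputed using last observation carried forward (LOCF) method"), and SAP 6.1 extends it to efficacy data generally: "The primary method of handling missing efficacy data will be the method of last observation carried forward (LOCF) imputation". No second method or sensitivity analysis is specified.

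The shell for the primary MITT table (14.2.1.1) carries the footnote "Note: Last observation carried forward (LOCF) used to impute missing values". The MITT shells for the secondary composites (14.2.2.1.1) and for subject therapeutic cure (14.2.3.1.1) carry the same note, as do the per-protocol versions. These shells have only Achieved and Not Achieved rows, with no n row.

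Therapeutic cure needs a negative culture plus a score of 0 for pruritus, debris, fungal elements and pain at Test of Cure (TOC). Protocol Table 1, footnote g, sets the culture visits: "For both fungi and bacteria at the Screening/Baseline visit and for fungi only at the End of Treatment and Test of Cure visits". Day 8 is End of Treatment (EOT) in the 7-day arm. In the 14-day arms it is an On Treatment visit, and the procedure list in protocol 6.2.2 contains no culture.

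For subjects who leave early, protocol 6.4 asks for the TOC procedures if possible. SAP 6.1.3 adds: "Data from early termination and unscheduled visits will be summarized based on mapped visit values".

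**The concern.** There are two effects.

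- **Unobserved cures.** EOT is nominally one day after the last dose and TOC eight days after. The endpoint is cure at the later visit. Under LOCF, a subject clear at EOT and never seen at TOC is reported as cured at TOC, in any arm.
- **Scoring that depends on duration.** For endpoints that include culture, the value available to carry forward from Day 8 differs by arm. The same dropout pattern can be a cure in one duration and not in the other.

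The second effect bears on the 7- versus 14-day comparison. Active versus vehicle share one schedule, so they are affected only if dropout, or change after EOT, differs between them. Clinical cure alone uses no culture, so a Day 8 dropout is scored alike in all arms. The study is descriptive, so what is at stake is a misread cure rate, not a false test result.

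**Working it through.** **Step 1. Apply the rule to one course of events.** The subject is clear on everything from Day 8 and last seen at Day 8, with no early-termination culture.

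| | 7-day arm | 14-day arms |
|---|---|---|
| Scheduled cultures | Days 1, 8, 15 | Days 1, 15, 22 |
| Signs and symptoms carried | Day 8, clear | Day 8, clear |
| Culture carried, baseline eligible | Day 8, negative | Day 1, positive |
| Therapeutic cure, baseline eligible | Achieved | Not achieved |
| Therapeutic cure, baseline not eligible | Achieved | Cannot be scored |

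The 14-day subject was still on treatment, so not achieved need not be the wrong score. The defect is that the score depends on the arm.

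**Step 2. Expected size.** The documents give no dropout or cure rates, so every input here is assumed:

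- d1, share last seen at Day 8: 5, 10, 15%
- d2, share of 14-day subjects last seen at Day 15: 0, 5, 10, 15%
- c, cure at TOC, equal in both durations: 30, 40, 50, 60%
- q8 and q15, clear at EOT on Day 8 (7-day arm) and on Day 15 (14-day arm): 30, 40, 50, 60% each
- u, share of 14-day Day 8 dropouts with a usable early-termination culture, who are then scored cured at rate q8: 0, 0.5, 1

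LOCF cure rates:

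- 7-day: (1 - d1)c + d1·q8
- 14-day: (1 - d1 - d2)c + d2·q15 + u·d1·q8
- Gap, 7-day minus 14-day: d1·q8·(1 - u) + d2·(c - q15)

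The grid has 3 × 4 × 4 × 4 × 4 = 768 cells for each u. The minimum is always at d1 5%, d2 15%, c 30%, q8 30%, q15 60%. The maximum is always at d1 15%, d2 15%, c 60%, q8 60%, q15 30%.

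| u | Minimum (points) | Maximum (points) | Cells +/0/- |
|---|---|---|---|
| 0 | 1.5 - 4.5 = -3.0 | 9.0 + 4.5 = +13.5 | 738/13/17 |
| 0.5 | 0.75 - 4.5 = -3.75 | 4.5 + 4.5 = +9.0 | 684/22/62 |
| 1 | 0 - 4.5 = -4.5 | 0 + 4.5 = +4.5 | 216/336/216 |

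**Step 3. Whole subjects.** Protocol 3.1 aims for about 10 evaluable subjects per group. Take 10 completers per arm with 5 cured in each, and add dropouts.

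- One subject per arm lost after a clear Day 8: LOCF gives 6/11 v 5/11, +9.1 points, if the 14-day subject counts as Not Achieved. If that subject is left out, it gives 6/11 v 5/10, +4.5. Missing = not cured and observed-case both give 0.
- One 14-day subject lost after a clear Day 15: LOCF gives 5/10 v 6/11, -4.5. Missing = not cured gives 5/10 v 5/11, +4.5. Observed-case gives 0.

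For scale, the 95% half-width for a difference at 5/10 per arm is 1.96 × √(2 × 0.25/10) = 0.438, about 44 points.

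**Step 4. Does missing = not cured remove the gap?** The rates become (1 - d1)c and (1 - d1 - d2)c, so a gap of d2·c remains in favour of 7 days (0 to 9.0 points on the grid). In absolute size it exceeds the LOCF gap in 256 of 768 cells at u = 0, 452 at u = 0.5 and 540 at u = 1. Observed-case has no expected gap only if dropout is unrelated to outcome.

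**Step 5. Can the planned tables recover composite cure?** The by-visit MITT shells (14.2.2.3.1 to 14.2.2.7.1) give TOC counts by component without an LOCF note. If each of five components is clear in k of 10 subjects, composite cure lies between max(0, 5k - 40) and k: 0 to 8 for k = 8, and 5 to 9 for k = 9. The component tables therefore do not determine it.

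**The case against.** The best defence is that the plan already limits the problem. Protocol 4.4 and 6.4 ask for TOC procedures, including culture, at early termination. SAP 6.1.3 drops an early-termination value "if no analyses are planned for the assessment at the mapped visit", but shell 14.2.2.3.1 has an On Treatment culture row for the 14-day arms. An analysis is therefore planned and that clause need not remove a culture from Days 4-11. Early-termination visits on Days 12-18 map to Day 15, where 14-day culture is scheduled. This stands as a consistent reading, and it is why u is varied above. It does not settle the matter: the procedures are only to be done if possible, and a separate clause in SAP 6.1.3 excludes early-termination data when scheduled data exist at the mapped visit.

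It is also fair that per-protocol membership mostly requires TOC attendance, that the listings allow a rebuild by hand, and that no hypothesis is tested. These are partial checks and they lower the stakes. None of them tabulates MITT composite cure without LOCF.

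Two stronger readings are tempting but not supported:

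- **That observed 7-day results on Days 19-23 are discarded because those days map to Day 22.** The TOC window ("This visit may occur up to 1 day sooner or up to 8 days later than the specified day") covers Days 14-23 in that arm. Protocol 6.5 puts a visit meant to serve as TOC on the TOC form, and SAP 6.1.3 then uses the nominal visit. The loss arises only if a site records the visit as early termination or unscheduled.
- **That the protocol contradicts itself on imputation.** The sentence in protocol 10.1 and the synopsis ruling out imputation closes a paragraph on by-visit descriptive summaries. It can be read as limited to them, and the table notes fit that reading.

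**Conclusion.** The point holds. Followed as written, the plan can report cures not observed at TOC, and for endpoints that include culture it can give a Day 8 dropout a score that depends on treatment duration.

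A reader might infer that LOCF favours the 7-day arm. The documents do not support a direction. The mostly positive gaps at u = 0 come from assuming that no 14-day Day 8 dropout has a usable culture; at u = 1 positive and negative cells are equal in number. All ranges rest on assumed rates and on no true difference in TOC cure. One dropout per arm can move the comparison by up to 9.1 points at the planned size, which is small beside a half-width of about 44 points.

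Nor should missing = not cured be taken as the unbiased answer. It reports no unobserved cure, but its own gap in favour of 7 days can be larger than the LOCF gap. The case for change is that three percentages are the main output, and the plan does not show how far they rest on carried-forward values.

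**What to change.** **Main change.** In SAP 6.1.5 and Tables 14.2.1.1, 14.2.2.1.1 and 14.2.3.1.1, present MITT results side by side as LOCF, missing = not cured, and observed-case, with an n row. Add per-arm counts of missing TOC and of the visit from which each carried value came. Read the 7- versus 14-day comparison as robust only if the three agree. State beside the not-cured column that it leaves a gap favouring 7 days, equal to the share of 14-day subjects lost after Day 15 times the TOC cure rate. Align protocol 10.5.4.

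**Secondary clarifications.**

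- State whether baseline may be carried forward and whether components from different visits may be combined.
- Confirm that an early-termination culture on Days 4-11 in the 14-day arms is used, as shell 14.2.2.3.1 implies.
- State that a 7-day early-termination or unscheduled visit inside that arm's TOC window counts as TOC.
- If that is the intent, say that the no-imputation sentence in protocol 10.1 and the synopsis covers only the by-visit summaries.

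**Cost.** Some rewording and a few more columns, with no new data. Cure rates will be slightly lower in the not-cured column.
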